8.1.2 Dose Escalation and Dose Adjustments

The daily volumes of IMP solution to be taken will be calculated based on the patients' weight and the dosing schedule will be provided to the caregiver. Further information on dispensing procedures will be provided in a separate Pharmacy Manual.

Caregivers will be trained on dose administration at Visit 2 (Day 1). Each patient will take their first dose of IMP at the clinic at the end of Visit 2 (Day 1). The investigator

Study Code: GWND18064

EudraCT Number: 2018-003370-27

Clinical Protocol 4.1, 07Jul2020 (duplicate synopsis removed)

will observe IMP administration by the caregiver at Visit 2 and verify that IMP was correctly administered, and that the patient did not aspirate. If an unacceptable AE develops at any time during the dose escalation period(s), dosing should initially be suspended or amended, at the investigator's discretion and in a blinded manner, until the event has resolved or is well tolerated. Patients who have escalated above 5 mg/kg/day should return to the previous dose level tolerated in steps of 5 mg/kg/day each week, unless a faster reduction is judged to be required for safety reasons. If a patient cannot tolerate 5 mg/kg/day, doses should be reduced to 2.5 mg/kg/day. If necessary, dosing may be temporarily suspended.

Patients whose dose has been decreased can have their dose increased again, if the tolerability improves. Patients unable to tolerate the target dose may stay at a lower dose. However, if a patient cannot tolerate a dose of 2.5 mg/kg/day the patient should permanently discontinue IMP treatment, unless a lower dose level is agreed in discussion with the medical monitor and can be accurately measured (minimum single dose volume 0.1 mL). Dose adjustments should be discussed with the GW medical monitor. The final decision regarding dose adjustments should be taken by the investigator. During the maintenance period, patients should continue on a stable dosing regimen at the target dose level. If that dose becomes poorly tolerated, the investigator may consider temporarily or permanently reducing the dosage for the remainder of the maintenance period; dose adjustments should follow the guidance above. However, where possible, the patient should be encouraged to return to the target dose level.

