- Continuing.
- Patient died.

D) Severity

When describing the severity of an AE the terms mild, moderate, or severe should be used. Clinical judgment should be used when determining which severity applies to any AE.

If the severity of an AE fluctuates day-to-day, e.g., a headache or constipation, the change in severity should not be recorded each time; instead, only the worst observed severity should be recorded with AE start and stop dates relating to the overall event duration, regardless of severity.

A severe AE is not the same as a SAE. For example, a patient may have severe vomiting, but the event does not result in any of the SAE criteria above. Therefore, it should not be classed as serious.

E) Causality

See [Section 12.5](#) above.

Study Code: GWND18064

EudraCT Number: 2018-003370-27

Clinical Protocol 4.1, 07Jul2020 (duplicate synopsis removed)

F) Action Taken with Trial Medication

This question refers to the action taken with the IMP due to an AE. The action with the IMP must be classed as:

- Not applicable, patient is not taking IMP.
- Dose not changed.
- Dose reduced.
- Trial medication interrupted.
- Trial medication stopped.

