#### **6.1.9.1 Adverse events**

A TEAE is defined as an AE with a start date on or after the first dose of IMP. If an AE has a partial start date and it is unclear from the partial date (or the stop date) whether the AE started prior to or post first dose of IMP then the AE will be considered treatment emergent. If the start date of the AE is the same as the date of first dose of IMP then the AE will be considered treatment emergent.

A TEAE will be considered treatment-related if the plausibility relationship to IMP is recorded on the eCRF as ‘yes’. If the data on plausibility relationship to IMP is missing then the TEAE will be considered treatment-related.

A TEAE will be considered leading to permanent discontinuation of IMP (leading to withdrawal) if the action taken with IMP is recorded on the eCRF as ‘trial medication stopped’ or the outcome is recorded on the eCRF as ‘patient died’.

A treatment-related TEAEs leading to withdrawal is a TEAE leading to permanent IMP

discontinuation and considered treatment-related as per above definition.

A TEAE will be considered leading to IMP temporary discontinuation if the action taken with IMP is recorded on the eCRF as 'trial medication interrupted'.

A TEAE will be considered leading to permanent IMP dose reduction excluding permanent discontinuation if the action taken with IMP is recorded on the eCRF as 'dose reduced'.

An AE will be considered fatal if the outcome is recorded on the eCRF as 'patient died'.

The time to first onset of AE will be calculated for TEAEs as:

Start date of AE – Date of first dose of IMP + 1

The time to AE resolution will be calculated for TEAEs as:

Stop date of AE – Start date of AE + 1

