## **9. Safety and Tolerability Analysis**

### **9.1 Adverse Events**

All reported AEs will be classified by system organ class (SOC), preferred term and lower level term using Version 21.1 of MedDRA or higher.

Summaries will be presented by treatment group as well as SOC and preferred term.

The following summaries will be generated (counts are by patient unless specified otherwise):

Overall summary of AEs, including number of patients reporting each of; Treatment Emergent Adverse Events (TEAEs), TEAEs that started during the titration period as applicable, treatment-related TEAEs, treatment-related TEAEs that started during the titration period, TEAEs leading to withdrawal, treatment-related TEAEs leading to withdrawal, serious TEAEs, treatment-related serious TEAEs.

- Summary of TEAEs.
- Summary of TEAEs by event (PT).
- Summary of treatment-related TEAEs.
- Summary of treatment-related TEAEs by event
- Summary of TEAEs by maximal severity.
- Summary of TEAEs by sex.
- Summary of serious TEAEs.
- Summary of serious TEAEs by event.
- Summary of non-serious TEAEs.
- Summary of non-serious TEAEs by event (PT).
- Summary of treatment-related serious TEAEs.
- Summary of treatment-related serious TEAEs by event (PT).
- Summary of TEAEs leading to permanent discontinuation of IMP.
- Summary of treatment-related TEAEs leading to permanent discontinuation of IMP.

- Summary of TEAEs leading to IMP dose reduction excluding permanent discontinuation (by resolution and overall).
- Summary of treatment-related TEAEs leading to IMP dose reduction excluding permanent discontinuation (by resolution and overall).
- Summary of TEAEs leading to temporary IMP dose reduction (by resolution and overall).
- Summary of treatment-related TEAEs leading to temporary IMP dose reduction (by resolution and overall).
- Summary of TEAEs leading to permanent IMP dose reduction excluding permanent discontinuation (by resolution and overall).
- Summary of treatment-related TEAEs leading to permanent IMP dose reduction excluding permanent discontinuation (by resolution and overall).
- Summary of fatal TEAEs.
- Summary of TEAEs by time of first onset of AE.
- Summary of TEAEs by time to AE resolution.
- Summary of TEAEs reported in  $\geq 2\%$  of patients (after rounding) in the GWP42003-P treatment groups and where the incidence is greater than the (pooled) placebo treatment group.
- List of patients experiencing TEAEs by SOC and preferred term.
- Summary of pre-treatment AEs.

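### The SAP labels any adverse event with the action 'dose reduced' as a permanent dose reduction, so a reduction that was later reversed would be tabulated as permanent

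*SAP*

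**What the plan says.** SAP 6.1.9.1 derives three categories from the action taken with the study drug:

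- *Permanent discontinuation*: action 'trial medication stopped', or outcome 'patient died'.
- *Temporary discontinuation*: "A TEAE will be considered leading to IMP temporary discontinuation if the action taken with IMP is recorded on the eCRF as" 'trial medication interrupted'.
- *Permanent dose reduction*: a TEAE is "considered leading to permanent IMP dose reduction excluding permanent discontinuation if the action taken with IMP is recorded on the eCRF as" 'dose reduced'. No condition on duration or later re-escalation is attached.

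The source field is in Protocol 12.6, item F: "The action with the IMP must be classed as" one of five options. These are not applicable, dose not changed, dose reduced, interrupted and stopped. Only one of them is a reduction.

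Protocol 8.1.2 treats reductions as possibly reversible. In the maintenance period "the investigator may consider temporarily or permanently reducing the dosage for the remainder of the maintenance period". It also states: "Patients whose dose has been decreased can have their dose increased again, if the tolerability improves", and "However, where possible, the patient should be encouraged to return to the target dose level".

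SAP 9.1 plans six dose-reduction tables: dose reduction overall (excluding permanent discontinuation), temporary dose reduction and permanent dose reduction, each for all TEAEs and for treatment-related TEAEs.

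**The concern.** The protocol separates temporary from permanent reductions. The action field does not, and the SAP puts the single recorded code under the word 'permanent'. A reader of the resulting table would take it as a count of reductions that lasted.

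The SAP states that all analysis is now descriptive (SAP 1 and 8), so table titles carry much of the message. Protocol 3.3.2 presents the lower dose as one that could be better tolerated, and Protocol 13.6.3.2 keeps the dose groups separate to explore dose effects on safety. Whether event-driven reductions persisted or were reversed bears on that comparison.

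The table list and the rules also use different names, so a programmer must guess what fills some of the tables.

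**Working it through.** No formula applies. The check maps each recorded action through the SAP rule to the planned tables.

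| Action recorded (Protocol 12.6 F) | Category in SAP 6.1.9.1 | Tables of that name in SAP 9.1 |
|---|---|---|
| Stopped (or outcome 'patient died') | Permanent discontinuation | 2 |
| Interrupted | Temporary discontinuation | 0 |
| Dose reduced | Permanent dose reduction | 2 |
| No matching option | No rule | Temporary dose reduction: 2 |
| No matching option | No rule | Dose reduction overall: 2 |

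**Counts.** SAP 9.1 has 26 bulleted items, of which 3 types × 2 = 6 concern dose reduction. There are 3 action rules and 4 action-based title types (permanent discontinuation plus the three reduction types). Two names match: permanent discontinuation and permanent dose reduction. That leaves 4 − 2 = 2 title types, or 2 × 2 = 4 tables, without a rule of that name, and 3 − 2 = 1 rule without a table of that name. The protocol's minimum set (13.6.3.2) has 7 summaries, and 0 of them concern dose reduction.

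**A reversed reduction.** Take two hypothetical patients whose dose is reduced for an event that then resolves. One returns to the target dose and the other stays on the lower dose. Both have action 'dose reduced' and outcome 'recovered', so both are classed as permanent dose reduction.

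**Does the by-resolution layout separate them?** No. SAP 9.1 bases it on the outcome of the event: recovered (with or without sequelae) against continuing, died or missing. Both patients fall under 'Resolved'.

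**The temporary tables.** Two readings are possible.

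1. *Interruptions feed them.* The tables are then populated, but interruptions are titled as reductions.
2. *Only a rule of that name may feed them.* The tables then have no stated source.

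Under neither reading does a reversed 'dose reduced' event appear as temporary.

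**Fatal outcome.** A TEAE with action 'dose reduced' and outcome 'patient died' meets both the reduction rule and the permanent-discontinuation rule. The reduction category is named as excluding permanent discontinuation, but the SAP does not say which rule takes precedence.

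**The case against.** The strongest reply is that the intended mapping can be inferred: interrupted means temporary, reduced means permanent, and the overall dose-reduction tables are the union. This accounts for all six tables. Protocol 8.1.2 also covers temporary suspension within its dose-adjustment guidance, so listing interruptions with reductions would be loose naming. The separate table shells, which the SAP says hold the full table detail, may state this mapping. This stands for the temporary tables: the gap there is probably a label mismatch, and one sentence or footnote could settle it. It does not help the permanent tables, where the same mapping leaves a reversed reduction under 'permanent'.

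SAP 6.1.9 lets further derived variables be documented only in programs. That covers additional variables. Permanent dose reduction is already defined, so a program that moved some 'dose reduced' events to temporary would contradict SAP 6.1.9.1.

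Materiality is low, and this also stands. The tables are descriptive and all collected data are to be listed (SAP 6, 6.1.10 and 9.1). SAP 7.4 summarises dose escalations and decreases separately, although it does not link them to adverse events. These outputs may let a reader trace a reversal, but they do not correct a table title.

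A reader might infer that the permanent tables certainly overstate lasting reductions. The documents do not show this: re-escalation is permitted and encouraged, but nothing shows that any reduction was reversed, and the trial was discontinued early. A reader might also infer that both permanent tables hold every 'dose reduced' event. They do not: one is restricted to treatment-related events, and events with a fatal outcome may be excluded.

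**Conclusion.** The point holds as a labelling error in the SAP with conditional consequences. As written, the rule would place any reversed reduction in the permanent-dose-reduction tables, subject to the unresolved overlap with fatal outcomes. The number of such events cannot be derived from the documents and could be zero. The temporary-dose-reduction tables lack a rule of that name. To say that they have no source at all would go too far, since interruptions are the likely source.

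The reach is six descriptive safety tables. No efficacy result and none of the seven protocol-minimum summaries is touched. The conclusion assumes that the eCRF carries the five options printed in the protocol. The eCRF, shells and programs were not available for this check. The point is worth correcting but has low priority.

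**What to change.** In SAP 6.1.9.1:

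- Rename the rule 'TEAE leading to IMP dose reduction', defined as action 'dose reduced' and excluding TEAEs that meet the permanent-discontinuation rule. This also settles the precedence for fatal outcomes.
- Keep 'trial medication interrupted' as temporary discontinuation (interruption).

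In SAP 9.1, retitle the tables to match, each for all and for treatment-related TEAEs:

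- dose reduction;
- interruption;
- if wanted, the two combined, excluding permanent discontinuation.

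Use a temporary/permanent split of reductions only if existing dose records can be linked to the adverse event and show whether the dose was restored. Otherwise drop the split.

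The cost is editing SAP wording, table titles, shells and programs. Relabelling needs no new data. Keeping the split would need a link between events and dose records that the documents do not show.

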#### **6.1.9.2 Prior and concomitant medications**

Medications that started and stopped prior to the first study drug intake will be considered prior medications. A concomitant medication is defined as any medication that was administered during the treatment period. This includes medications that started before the treatment period and continued while on treatment and medications that started during the treatment period.

If the start/stop dates of a medication are partially or completely missing, then the medication will be assumed to be concomitant if it cannot be definitely shown that it was not administered during the treatment period. Missing dates will not be replaced.

#### **6.1.9.3 Age**

Age will be calculated as:

(Date of screening – date of birth) ÷ 365.25.

#### **6.1.9.4 Exposure**

The total number of dosing days in the treatment period will be calculated as:

(Date of last dose in the treatment period – Date of Day 1) + 1

### **6.1.10 Data Adjustments/Handling/Conventions**

All collected data will be presented in listings. Data not subject to analysis according to this plan will not appear in any tables or graphs but will be included only in the data listings.

## **7. Study Patients and Demographics**

### **7.1 Disposition of Patients and Withdrawals**

Patient disposition, by site, by country and overall, will be summarized by treatment group and overall using standard summary statistics. The number screened, number of screen failures and number randomized will be included.

A screen failure disposition table will be presented, including number of patients screened, number failing screening, number randomized and the reasons for failing screening.

Patient disposition, including patients treated, patients who completed the treatment period and the taper phase, patients entering the OLE, patients discontinued (including reason for discontinuation) from the treatment but completed trial, patients that withdrew from trial, and taper phases will be summarized by absolute counts (n) and percentages (%). A further table split by site, and by country will be produced, showing number of patients randomized, withdrawn and completed the treatment period and entering the OLE at each site or in each country.

## 7.2 Protocol Deviations

Protocol deviations will be identified and classified.

Major protocol deviations will be summarized by type of violations for the randomized population.

Protocol deviations will be listed. Protocol deviations due to COVID-19 will be listed separately.

## 7.3 Demographics and Other Baseline Characteristics

The following demographic data will be summarized by treatment group and overall for the safety and ITT analysis sets:

- Age (years);
- Age group (2-5 years, 6-12 years and 13-18 years);
- Sex;
- Race;
- Ethnicity
- Country;
- Region (United States, Rest of the World);
- Weight at baseline (kg);
- Height at baseline (cm);
- Body mass index at baseline (kg/m^2);

The following baseline characteristics will be summarized by treatment group and overall for the safety and ITT analysis sets:

- CSS Score;
- CSS stratum;
- Previous use of cannabis.

### 7.3.1.1 History of RTT

The following history of RTT data will be summarized by treatment group and overall for the safety analysis set:

- Type of diagnosis (Typical, Atypical).
- Main and supportive criteria for RTT diagnosis.
- Age at diagnosis (months)
- Time since last known loss of hand use or verbal language or gross motor regression (months).

- Information about the *MECP2* mutation (whether a known mutation is documented and if available, the type of mutation).
- Communication methods used by the child.
- Types of seizures that are ongoing.
- Status epilepticus.
- Whether the child lives at home or at a care home/institution.
- Most common feeding method.
- Planned method for IMP administration.

### **7.3.2 Medical and Surgical History and Current Medical Conditions**

All conditions and diagnoses on the ‘medical and surgical history’ eCRF page will be coded using Version 21.1 of the Medical Dictionary for Regulatory Activities (MedDRA v21.1) or later version.

The number of patients with relevant or significant medical or surgical history and medical history by system organ class, and preferred term, will be summarized by absolute counts (n) and percentages (%). Percentages will be calculated based on the number of patients in the specific treatment group. Two tables will be produced, one including any events classified as resolved at screening, and the other including all current conditions.

### **7.4 Exposure and Compliance**

IMP is to be administered twice daily (morning and evening). The first dose will be taken in the clinic on Day 1. The date of final dose in the treatment period will be recorded on the eCRF. The date of final dose, for patients who enter the taper period, will be recorded on the eCRF at the end of taper visit.

For dosing during the treatment period, the following data will be presented: total number of dosing days, number of days with diary reported, number of days with doses not taken according to the diary will be reported as continuous variables. Number and percentages of dose adjustments (escalation, decrease, other) as well as methods of IMP administration will be described.

## **8. Efficacy Analysis**

The primary analyses will use the ITT analysis set.

No formal hypothesis testing will be carried out for this study. Statistical analysis will be descriptive.

### **8.1 Primary Efficacy Endpoint**

The RSBQ is a caregiver-completed questionnaire that measures the frequency of current disease characteristics (45 items) that may or may not apply to the patient. Each item is rated on a 3-point numerical scale, where all items except for item 31 (“Uses eye gaze to convey feelings, needs and wishes”) is scored as follows: 0 indicating an item that is ‘not true as far as you know’, 1 indicating an item is ‘somewhat or sometimes true’, and 2 indicating an item that is ‘very true or often true’. Item 31 is to be reverse scored, where 0 indicates that this item is ‘very true or often true’, 1

indicating that this item is ‘somewhat or sometimes true’, and 2 indicating that this item is ‘not true as far as you know’. The total maximum score is 90 and higher total scores represent greater severity.

The RSBQ score and its change from baseline will be summarized on a numerical scale by visit and treatment group.

## 8.2 Key Secondary Efficacy Endpoint

The CGI-I is a 7-point scale that requires the clinician to assess how much the patient’s illness has improved or worsened relative to a baseline state at the beginning of the intervention. This is rated as: 1 = very much improved; 2 = much improved; 3 = minimally improved; 4 = no change; 5 = minimally worse; 6 = much worse; or 7 = very much worse.

The CGI-I score will be summarized on both a categorical scale and a numerical scale by visit and treatment group.

The analyses described above will be performed on the ITT analysis set.

## 8.3 Other Secondary Efficacy Endpoints

### 8.3.1 RSBQ Subscales

The RSBQ includes 8 subscales: general mood, breathing problems, hand behaviors, face movements, body rocking/expressionless face, night-time behaviors, anxiety/fear, and walking/standing. The items included in each subscale are presented in [Table 4](#).

**Table 4 RSBQ Subscales**

Subscale	Items Included
General Mood	2, 14, 15, 16, 22, 29, 30, 36
Breathing Problems	1, 5, 6, 19, 25
Hand Behaviors	18, 20, 21, 24, 35, 43
Face Movements	4, 28, 32, 34
Body Rocking/Expressionless Face	12, 17, 31*, 33, 40, 41
Night-time Behaviors	13, 37, 42
Anxiety/Fear	7, 9, 10, 38
Walking/Standing	23, 39

\* Item 31 is to be reverse scored as described in section 5.5.2.

The subscale scores are calculated by summing the scores of the items in each subscale.

Subscale scores and their change from baseline will be summarized by treatment and visit for each subscale.

The analysis will be performed on the ITT analysis set.

### 8.3.2 Caregiver Global Impression of Severity

The CGI-S is a 7-point scale that requires the clinician to rate the severity of the patient’s illness at the time of assessment, relative to the clinician’s experience with patients who have the same diagnosis. Considering total clinical experience, a patient will be assessed on severity of illness at

the time of rating. This is rated as: 1 = normal, not at all ill; 2 = borderline ill; 3 = mildly ill; 4 = moderately ill; 5 = markedly ill; 6 = severely ill; or 7 = extremely ill.

CGI-S scores and their change from baseline will be summarized by treatment and visit. Frequency table will be created for CGIS categories by treatment and visit.

